5.4 IMMEDIATE REPORTING REQUIREMENTS FROM INVESTIGATOR TO SPONSOR

Certain events require immediate reporting to allow the Sponsor to take appropriate measures to address potential new risks in a clinical trial. The investigator must report such events to the Sponsor immediately; under no circumstances should reporting take place more than 24 hours after the investigator learns of the event. The following is a list of events that the investigator must report to the Sponsor within 24 hours after learning of the event, regardless of relationship to study drug:

- Serious adverse events (defined in Section [5.2.2](#); see Section [5.4.2](#) for details on reporting requirements)

- Adverse events of special interest (defined in Section 5.2.3; see Section 5.4.2 for details on reporting requirements)
- Pregnancies (see Section 5.4.3 for details on reporting requirements)

The investigator must report new significant follow-up information for these events to the Sponsor immediately (i.e., no more than 24 hours after becoming aware of the information). New significant information includes the following:

- New signs or symptoms or a change in the diagnosis
- Significant new diagnostic test results
- Change in causality based on new information
- Change in the event's outcome, including recovery
- Additional narrative information on the clinical course of the event

Investigators must also comply with local requirements for reporting serious adverse events to the local health authority and IRB/EC.

5.4.2 Reporting Requirements for Serious Adverse Events and Adverse Events of Special Interest

5.4.2.1 Events That Occur prior to Study Drug Initiation

After informed consent has been obtained but prior to initiation of study drug, only serious adverse events caused by a protocol-mandated intervention should be reported. The paper Clinical Trial Serious Adverse Event/Adverse Event of Special Interest Reporting Form provided to investigators should be completed and submitted to the Sponsor or its designee immediately (i.e., no more than 24 hours after learning of the event), either by faxing or by scanning and emailing the form using the fax number or email address provided to investigators.

5.4.2.2 Events That Occur after Study Drug Initiation

After initiation of study drug, serious adverse events and adverse events of special interest will be reported until 28 days after the last dose of study drug. Investigators should record all case details that can be gathered immediately (i.e., within 24 hours after learning of the event) on the Adverse Event eCRF and submit the report via the

electronic data capture (EDC) system. A report will be generated and sent to Roche Safety Risk Management by the EDC system.

In the event that the EDC system is unavailable, the paper Clinical Trial Serious Adverse Event/Adverse Event of Special Interest Reporting Form provided to investigators should be completed and submitted to the Sponsor or its designee immediately (i.e., no more than 24 hours after learning of the event), either by faxing or by scanning and emailing the form using the fax number or email address provided to investigators. Once the EDC system is available, all information will need to be entered and submitted via the EDC system.

Instructions for reporting serious adverse events that occur >28 days after the last dose of study treatment are provided in Section 5.6.

5.4.3 Reporting Requirements for Pregnancies

5.4.3.1 Pregnancies in Female Patients

Female patients of childbearing potential will be instructed to immediately inform the investigator if they become pregnant during the study or within 28 days after the last dose of study drug. A paper Clinical Trial Pregnancy Reporting Form should be completed and submitted to the Sponsor or its designee immediately (i.e., no more than 24 hours after learning of the pregnancy), either by faxing or by scanning and emailing the form using the fax number or email address provided to investigators. Pregnancy should not be recorded on the Adverse Event eCRF. The investigator should discontinue study drug and counsel the patient, discussing the risks of the pregnancy and the possible effects on the fetus. Monitoring of the patient should continue until conclusion of the pregnancy. Any serious adverse events associated with the pregnancy (e.g., an event in the fetus, an event in the mother during or after the pregnancy, or a congenital anomaly/birth defect in the child) should be reported on the Adverse Event eCRF. In addition, the investigator will submit a Clinical Trial Pregnancy Reporting Form when updated information on the course and outcome of the pregnancy becomes available.

5.4.3.2 Pregnancies in Female Partners of Male Patients

Male patients will be instructed through the Informed Consent Form to immediately inform the investigator if their partner becomes pregnant during the study or within 28 days after the final dose of study drug. A paper Clinical Trial Pregnancy Reporting Form should be completed and submitted to the Sponsor or its designee immediately (i.e., no more than 24 hours after learning of the pregnancy), either by faxing or by scanning and emailing the form using the fax number or email address provided to investigators. Attempts should be made to collect and report details of the course and outcome of any pregnancy in the partner of a male patient exposed to study drug. When permitted by the site, the pregnant partner would need to sign an Authorization for Use and Disclosure of Pregnancy Health Information to allow for follow-up on her pregnancy. If the authorization has been signed, the investigator should submit a Clinical Trial

Pregnancy Reporting Form when updated information on the course and outcome of the pregnancy becomes available. An investigator who is contacted by the male patient or his pregnant partner may provide information on the risks of the pregnancy and the possible effects on the fetus, to support an informed decision in cooperation with the treating physician and/or obstetrician.

5.4.3.3 Abortions

A spontaneous abortion should be classified as a serious adverse event (as the Sponsor considers abortions to be medically significant), recorded on the Adverse Event eCRF, and reported to the Sponsor immediately (i.e., no more than 24 hours after learning of the event; see Section 5.4.2).

If a therapeutic or elective abortion was performed because of an underlying maternal or embryofetal toxicity, the toxicity should be classified as a SAE, recorded on the Adverse Event eCRF, and reported to the Sponsor immediately (i.e., no more than 24 hours after learning of the event; see Section 5.4.2). A therapeutic or elective abortion performed for reasons other than an underlying maternal or embryofetal toxicity is not considered an adverse event.

All abortions should be reported as pregnancy outcomes on the paper Clinical Trial Pregnancy Reporting Form.

5.4.3.4 Congenital Anomalies/Birth Defects

Any congenital anomaly/birth defect in a child born to a female patient exposed to study drug should be classified as a serious adverse event, recorded on the Adverse Event eCRF, and reported to the Sponsor immediately (i.e., no more than 24 hours after learning of the event; see Section 5.4.2).

5.5 FOLLOW-UP OF PATIENTS AFTER ADVERSE EVENTS

5.5.1 Investigator Follow-Up

The investigator should follow each adverse event until the event has resolved to baseline grade or better, the event is assessed as stable by the investigator, the patient is lost to follow-up, or the patient withdraws consent. Every effort should be made to follow all serious adverse events considered to be related to study drug or trial-related procedures until a final outcome can be reported.

During the study period, resolution of adverse events (with dates) should be documented on the Adverse Event eCRF and in the patient's medical record to facilitate source data verification.

All pregnancies reported during the study should be followed until pregnancy outcome.

5.5.2 Sponsor Follow-Up

For serious adverse events, adverse events of special interest, and pregnancies, the Sponsor or a designee may follow up by telephone, fax, email, and/or a monitoring visit to obtain additional case details and outcome information (e.g., from hospital discharge summaries, consultant reports, autopsy reports) in order to perform an independent medical assessment of the reported case.

5.6 ADVERSE EVENTS THAT OCCUR AFTER THE ADVERSE EVENT REPORTING PERIOD

The Sponsor should be notified if the investigator becomes aware of any serious adverse event that occurs after the end of the adverse event reporting period (defined as 28 days after the last dose of study drug), if the event is believed to be related to prior study drug treatment. These events should be reported through use of the Adverse Event eCRF. However, if the EDC system is not available, the investigator should report these events directly to the Sponsor or its designee, either by faxing or by scanning and emailing the paper Clinical Trial Serious Adverse Event/Adverse Event of Special Interest Reporting Form using the fax number or email address provided to investigators.

5.7 EXPEDITED REPORTING TO HEALTH AUTHORITIES, INVESTIGATORS, INSTITUTIONAL REVIEW BOARDS, AND ETHICS COMMITTEES

The Sponsor will promptly evaluate all serious adverse events and adverse events of special interest against cumulative product experience to identify and expeditiously communicate possible new safety findings to investigators, IRBs, ECs, and applicable health authorities based on applicable legislation.

To determine reporting requirements for single adverse event cases, the Sponsor will assess the expectedness of these events using the following reference document:

- Baloxavir Marboxil Investigator's Brochure

The Sponsor will compare the severity of each event and the cumulative event frequency reported for the study with the severity and frequency reported in the applicable reference document.

Reporting requirements will also be based on the investigator's assessment of causality and seriousness, with allowance for upgrading by the Sponsor as needed.

An iDMC will monitor the incidence of the events listed in Section 5.2.3 during the study. An aggregate report of any clinically relevant imbalances that do not favor the test product will be submitted to health authorities.

6. STATISTICAL CONSIDERATIONS AND ANALYSIS PLAN

Efficacy analyses will be conducted for the modified intent-to-treat infected (mITTI) population. This is defined as all patients randomized who received at least one dose of study drug and were centrally assessed as RT-PCR positive for influenza at any timepoint, with patients grouped according to the treatment assigned at randomization.

Safety analyses will be conducted for the safety population. This is defined as all patients who received at least one dose of study drug, with patients grouped according to the treatment received.

The analysis will occur at the end of the study (as defined in Section 3.2).

Detailed specifications of the statistical methods will be described in the Statistical Analysis Plan (SAP).

The global population will include all patients enrolled during the global enrollment phase (If patients from China are enrolled, a China subpopulation will include all patients enrolled at *National Medical Products Administration [NMPA]*-recognized sites). Separate analyses *may* be performed for the global population and the China subpopulation (see Section 6.8 for information on the China subpopulation analyses).

6.1 DETERMINATION OF SAMPLE SIZE

Two new factors influenced the revised sample size: 1) the revised assumption for the placebo plus NAI control-arm TTCI following blinded data review (Section 6.1.1) and 2) the faster than anticipated enrollment rate. Integration of these two factors informed a sample size readjustment to approximately 366 randomized patients. Assuming that the RT-PCR-positive rate (tested in a central laboratory) will be 75% of the randomized population and a dropout rate of 4%, the modified intent-to-treat (influenza) infected (mITTI) population will be 264 patients (i.e., 176 patients in the baloxavir marboxil group and 88 in the placebo group). The total number of randomized patients may change based on the percentage of patients who are RT-PCR positive during the study.

The total mITTI sample size of 264 patients provides at least 80% power using the Logrank Chi-Square test to detect a 31-hour difference in TTCI between treatment groups under the following assumptions: median TTCI in the placebo plus NAI group is 94 hours, 840 hours follow-up (35 days) using 5% alpha. The minimal detectable difference is expected to be around 23 hours. The alteration of the TTCI in the placebo plus NAI group to 94 hours was selected after consideration of the response rates observed in a blinded review (see Section 6.1.1) of TTCI including data from 127 patients.

The increased sample size has the consequential benefit of a larger population for safety analysis of the combination and multiple dose regimen specifically tested in this study for the severely ill hospitalized patient group.

The study power is calculated based on the primary endpoint incorporating a group sequential design (GSD) using a beta spending function with non-binding rule, to allow for one futility interim, without increasing the overall experiment-wise error rate.

6.1.1 Blinded Sample Size Re-Assessment

The TTCI of 84 hours for the placebo plus NAI arm was selected in the initial study design (i.e., protocol version 1) after consideration of response rates observed in prior hospitalized studies with similar clinical response endpoints (Marty et al. 2017; de Jong et al. 2014).

After the first northern hemisphere flu season recruitment, a blinded evaluation of the protocol defined TTCI for all available data was conducted to improve the accuracy of assumptions of the length of TTCI in the placebo plus NAI group. The pooled median TTCI of this blinded review (94 hours) was selected as the revised assumption for the placebo plus NAI group, which resulted in the adjustment of the study sample size (Section 6.1).

Given the blinded nature of the evaluation, this has no impact on the overall alpha for the study.

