Determination of Sample Size

Two new factors influenced the revised sample size: 1) the revised assumption for the placebo plus NAI control-arm TTCl following blinded data review and 2) the faster than anticipated enrollment rate. Integration of these two factors informed a sample size readjustment to approximately 366 randomized patients. Assuming that the RT-PCR-positive rate (tested in a central laboratory) will be 75% of the randomized population and a dropout rate of 4% the mITTI population will be 264 patients (i.e., 176 patients in the baloxavir marboxil group and 88 in the placebo group).

The total number of randomized patients may change based on the percentage of patients who are RT-PCR positive during the study.

The total mITTI sample size of 264 patients provides at least 80% power using the Logrank Chi-Square test to detect a 31-hour difference in TTCl between treatment groups under the following assumptions: median TTCl in the placebo plus NAI group is 94 hours, 840 hours follow-up (35 days) using 5% alpha. The minimal detectable difference is expected to be around 23 hours. The alteration of the TTCl in the placebo plus NAI group to 94 hours was selected after consideration of the response rates observed in a blinded review of TTCl including data from 127 patients.

The increased sample size has the consequential benefit of a larger population for safety analysis of the combination and multiple dose regimen specifically tested in this study for the severely ill hospitalized patient group.

The study power is calculated based on the primary endpoint incorporating a group sequential design (GSD) using a beta spending function with non-binding rule, to allow for one futility interim, without increasing the overall experiment-wise error rate.

Interim Analyses

After approximately 65% of TTCl events, a formal unblinded non-binding futility interim analysis based on the TTCl will be performed. The futility interim analysis will use a Lan-DeMets Pocock beta spending function. If the hazard ratio seen at the interim is below the calculated futility bound, the trial may be declared futile and recruitment will be stopped.

The futility interim is non-binding on the Sponsor, and any deviation from the iDMC recommendation will be fully documented in the CSR. If the study is stopped for futility, at that point the study results will be reported. Full operating characteristics of the IA will be detailed in the SAP.

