4.2 METHOD OF TREATMENT ASSIGNMENT AND BLINDING

Following completion of screening and after all patient eligibility requirements are confirmed, patients will undergo randomization in a 2:1 ratio stratified by three regions (i.e., North America; Europe, Middle East, and Africa [EMEA]; and rest of world [ROW]), NEWS2 score (≤ 7 , > 7 ; see [Appendix 3](#)), and time from symptom onset to study treatment (≤ 48 hours, > 48 hours).

All patients will receive either baloxavir marboxil or its matching placebo.

A permuted-block randomization method will be used to obtain an approximate 2:1 ratio between the active treatment arm and the placebo arm within each stratum. The placebo and active kits are filled and packaged to look identical.

All study site personnel and patients will be blinded to the baloxavir marboxil versus placebo treatment assignment throughout the study; the SOC NAI will be open label. The Sponsor and its agents will also be blinded to the baloxavir marboxil assignment, with the exception of individuals who require access to patient treatment assignments to fulfill their responsibilities during a clinical trial. These roles include the unblinding group responsible, clinical supply chain managers, sample handling staff, operational assay group personnel, IxRS service provider, and iDMC members.

While PK samples must be collected from patients assigned to the comparator placebo arm, PK assay results for these patients are not needed for the safe conduct or proper interpretation of this study. Laboratories responsible for performing study drug PK assays will be unblinded to patients' treatment assignments in order to identify appropriate samples to be analyzed. PK samples from patients assigned to the placebo arm will not be analyzed for study drug PK concentration except by request (e.g., to evaluate a possible error in dosing).

If unblinding is necessary for a medical emergency (e.g., in the case of a serious adverse event for which patient management might be affected by knowledge of treatment assignment), the investigator will be able to break the treatment code by contacting the IxRS. The investigator is not required to contact the Medical Monitor prior to breaking the treatment code; however, the treatment code should not be broken except in emergency situations.

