2.4 DETERMINATION OF SAMPLE SIZE

The required sample size of the modified intent-to-treat infected (mITTI) population is 264 patients (176 patients in the baloxavir marboxil group and 88 in the placebo group). It is assumed that the reverse transcriptase polymerase chain reaction (RT-PCR)–positive rate (tested in a central laboratory) will be 75% of the randomized population; hence, approximately 366 patients will be randomized to ensure an adequate number of patients in the mITTI population and to allow for a 4% dropout rate. The total number of randomized patients may change based on the percentage of patients who are RT-PCR positive during the study.

The total mITTI sample size of 264 patients provides at least 80% power using the log-rank Chi-Square test to detect a 31-hour difference in the time to clinical improvement (TTCl) between treatment groups under the following assumptions: median TTCl in the placebo plus NAI group is 94 hours, 840 hours follow-up (35 days), using an alpha of 5%, and the minimal detectable difference is 23 hours. The TTCl in the placebo plus NAI group of 94 hours was selected after consideration of the response rates observed in a blinded review of TTCl including data from 127 patients.

The study power is calculated based on the primary endpoint incorporating a group sequential design (GSD) using a beta spending function with non-binding rule, to allow for one futility interim, without increasing the overall experiment-wise error rate.

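### The 94-hour placebo median is a pooled 2:1 value, so the claim of at least 80% power for a 31-hour benefit does not fit its own input (exponential model: about 59 to 66%, against 80 to 87% at 94 vs 63 h)

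*Protocol*

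**What the plan says.** Protocol 6.1.1 explains that, after one northern hemisphere season, a blinded evaluation "for all available data was conducted to improve the accuracy of assumptions of the length of" time to improvement on control. Its result was then carried into the design: the median over both arms combined, in that section's words, "of this blinded review (94 hours) was selected as the revised assumption for the placebo plus NAI group". It replaced the 84 h of the initial design, which had been chosen from prior studies in hospitalized patients.

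Protocol 6.1 then says that 264 mITTI patients (176 and 88) "provides at least 80% power using the Logrank Chi-Square test to detect a 31-hour difference" in TTCI, with a control median of 94 h, 840 h of follow-up and 5% alpha. It adds that power was calculated "incorporating a group sequential design (GSD) using a beta spending function with non-binding rule". SAP 2.4 repeats the claim.

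Protocol 4.2 states that "patients will undergo randomization in a 2:1 ratio stratified by three regions" and two further factors, so about two thirds of the reviewed patients would have been on baloxavir.

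Only Protocol 6.1.1 uses the word pooled. Protocol 6.1 and both copies of the synopsis say the median "in the placebo plus NAI group to 94 hours was selected after consideration of the response rates observed" when 127 patients were reviewed blind. SAP 2.4 says the figure "of 94 hours was selected after consideration of the response rates observed in a blinded review". None of these places adjusts the pooled value for a treatment effect or gives power at another control median.

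**The concern.** A pooled median equals the control median only if the drug does nothing. If baloxavir shortens TTCI, the pooled median lies between the two arm medians and the control median is above 94 h. That much needs no distributional model.

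The power claim is stated in hours. Holding the difference at 31 h while the control median rises makes the hazard ratio smaller than 94/63 = 1.49, and log-rank power depends on the hazard ratio. The sample size was revised from this input. A reader who takes the claim at face value would treat a non-significant result as stronger evidence against a 31-hour benefit than the design supports.

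**Working it through.** **Inputs.** Control median 94 h, difference 31 h (so 63 h on baloxavir), 264 mITTI patients at 2:1, 840 h follow-up: Protocol 6.1. Two-sided 5% tests: Protocol 6.4. Futility look at about 65% of events with Lan-DeMets Pocock beta spending: Protocol 6.7.1. Bound about p = 0.077: SAP 2.5.1. Pooled source of the 94 h: Protocol 6.1.1. Assumed here, because the documents do not say: exponential TTCI, the 0.077 bound one-sided, and reviewed patients representative of the mITTI population.

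**Step 1. Reproduce the plan's figure.**
- Patients: 366 × 0.75 × 0.96 = 263.5, so 264. With exponential times nearly all have an event by 840 h (263.8 of 264).
- Drift: θ = ln(HR) × √(264 × 2/9) = 0.4002 × 7.659 = 3.065.
- Without stopping: Φ(3.065 − 1.96) = 86.5%.
- Bound followed: P(Z₁ > 1.4255 and Z₂ > 1.96), where Z₁ has mean θ√0.65, Z₂ has mean θ, and their correlation is √0.65. Result: 80.3%.

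The design reproduces from the other side too. Beta spent at 65% is 0.2 × ln(1 + (e − 1) × 0.65) = 0.150. The drift needed for 80% power is 3.052, the one-sided futility p is 0.0772, and the inflation over a fixed design is 1.187. A fixed design needs 220.6 events at HR 1.49; 220.6 × 1.187 = 261.8, against 264 planned. So the bound-followed basis, the one-sided reading and the exponential model together recover the plan.

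**Step 2. What pooled median does 94 vs 63 h imply?** Solve (1/3)·2^(−x/94) + (2/3)·2^(−x/63) = 0.5. This gives x = 71.6 h, not 94 h.

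**Step 3. Set the pooled median to 94 h and keep 31 h.** Solve (1/3)·2^(−94/m) + (2/3)·2^(−94/(m − 31)) = 0.5. This gives m = 116.0 h for control and 85.0 h for baloxavir, HR 1.36. Drift is 0.3108 × 7.659 = 2.380. Power is 58.5% with the bound followed and 66.3% without stopping.

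**Step 4. Hold the hazard ratio instead.** HR 1.49 with a pooled median of 94 h means 123.5 vs 82.7 h, a difference of 40.7 h. Power stays at about 80% (87% without stopping).

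**Step 5. Simulation check.** A log-rank simulation (8,000 runs, 176/88, censoring at 840 h, one-year uniform accrual assumed) gave 78.6% and 85.5% at 94/63 h, and 56.9% and 64.7% at 116/85 h (bound followed, then no stopping).

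**Step 6. Dependence on the control median** (31-hour difference, exponential, closed form):

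| Control median (h) | 94 | 100 | 110 | 116 | 125 | 140 |
|---|---|---|---|---|---|---|
| Bound followed (%) | 80 | 74 | 64 | 59 | 51 | 41 |
| No stopping (%) | 87 | 81 | 72 | 66 | 59 | 48 |

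**Step 7. Dependence on the distribution** (Weibull shape k, HR = (ratio of medians)^k, bound followed):

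| Shape | 0.8 | 1.0 | 1.2 | 1.3 | 1.6 |
|---|---|---|---|---|---|
| Pooled 94 h, 31 h difference (%) | 41 | 59 | 75 | 81 | 94 |
| 94 vs 63 h (%) | 61 | 80 | 92 | 95 | 99 |

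For any shape, (m/(m − 31))^k falls as m rises, so the loss is always there. Power reaches 80% at shape about 1.28 with the bound followed and about 1.18 without stopping. At shape 1.28 the 94/63 h design would have needed only about 160 events with the futility look, so 264 points to exponential planning. That says nothing about the true distribution.

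**Step 8. Other uncertainty.** The standard error of a median from 127 uncensored exponential times is about 94/(0.693 × √127) = 12 h. Pooled values of 72 and 118 h, both within about two standard errors, give 80% and 41% with the bound followed. If 25% of those reviewed were uninfected and behaved like placebo (an assumption), the medians are about 111 vs 80 h, with power 63% and 71%.

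**The case against.** The strongest reply is that the plan contains no miscalculation. Power is stated conditionally on a 94-hour control median, and on that condition it is right. A blinded review can only give pooled data. Protocol 6.1 points to 6.1.1, where the pooled origin is disclosed, and the other places say the review was blinded, from which pooling can be inferred. All of this stands. What is missing is any allowance for the assumed effect.

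The move from 84 to 94 h was also in the cautious direction: the same model gives about 90% at 84 vs 53 h. A control median of 116 h is 38% above that prior value (116/84 = 1.38). This does not rule out 116 h, but it is a reason not to treat it as an estimate.

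The log-rank test responds to the hazard ratio, and SAP 4.5.1 defines the estimand as a difference in distributions. Power for HR 1.49 is therefore untouched. That is correct, but both documents state the power claim in hours and give no hazard ratio for it.

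A reader might infer that the trial's real power is 59%. The documents do not support that. SAP 2.5.1 makes the bound non-binding and also asks for iDMC agreement that there is no clinically meaningful difference, so 59% and 66% bracket the case. Nor does the SAP say whether 0.077 is one- or two-sided. The one-sided reading reproduces 80%; read as two-sided, the bound-followed figures are 73% at 94/63 h and 51% at 116/85 h.

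**Conclusion.** The concern holds as an inconsistency between the source of the control median and the power claim built on it. If baloxavir works and the reviewed patients represent the mITTI population, a 31-hour difference is a smaller relative effect than the plan's 1.49, and power for it is lower than the same model gives at 94 vs 63 h. Under exponential TTCI the figures are about 59% (bound followed) to 66% (no stopping), in place of 80% to 87%. A true 31-hour benefit would then be missed about 41% of the time rather than 20% with the bound followed, or 34% rather than 13% without stopping.

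The direction is firm, given a working drug and a representative review sample. The size is not: it rests on the exponential model, a pooled median of exactly 94 h, and the one-sided reading of the bound. At least 80% survives with the bound followed if the Weibull shape exceeds about 1.28. Two stronger conclusions do not follow. The documents do not show that the sample size must rise, because the design keeps its power for HR 1.49. They give no ground to question the type I error either, since the review was blinded and the test is unchanged.

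**What to change.** Keep the sample size, the test and the bound. In Protocol 6.1 and 6.1.1, SAP 2.4 and both copies of the synopsis:

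1. Label 94 h as the pooled median of blinded 2:1 data, not as an estimate for the placebo plus NAI arm.
2. Restate the power claim on explicit assumptions. Suggested content: assuming exponential TTCI, reviewed patients representative of the mITTI population, and the 0.077 futility bound read as one-sided, 264 mITTI patients give about 80% power (about 87% without stopping) for HR 1.49. With a pooled median of 94 h this corresponds to about 123 vs 83 h, or about 41 hours. For a 31-hour difference (about 116 vs 85 h) power is about 59% with the bound followed and about 66% without stopping.
3. Add a short table of power for 31 h at control medians from 94 to 140 h, recomputed by the sponsor with its own design software. The closed-form values in step 6 show what to expect.

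The cost is revised text and one table. The downside is that the stated power for 31 hours becomes less favourable and is shown to depend on the model. No patients are added.
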